6.2 Procedures

Vaccinations take place at the baby clinic / health center of the toddler. Prior to vaccination, the child health physician or nurse reviews the health status of the child to exclude any contra-indication for MenC and MMR vaccinations according to the guidelines of the National Immunisation Programme. These vaccinations are given to all eligible children, regardless of later (non)participation.

Health personnel at the baby clinic will record the vaccinations (name clinic, name and batch no of vaccine, date of vaccination) in the child health dossier, as well as on the vaccination cards, which are sent to the RIVM vaccination registry (DVP), as prescribed in the NIP.

After vaccination, parents are reminded to the letter that they received earlier, and that they still may sign-up for the study with the use of a reporting code. If they intend to participate, baby clinic staff will record the vaccines given at that day, specifically batch numbers, and injection sites. The letter also contains a diary table, to be used by the parents as an aide-memoire, to record any health event that is to be filled in the electronic questionnaires.

Parents of children who have registered to participate will receive a web-based questionnaire at day 5 after the vaccines were administered with questions about any ADRs that occurred within 4 days of vaccination. A second questionnaire will be sent after two weeks, and a third after 4 weeks.

6.3 Assessments / collection of data

6.3.1 Preregistration and registration

Upon receipt of the first letter parents may pre-register for the study by reporting their email address and scheduled vaccination date. At this date, Lareb will send them an email with a link enabling the parents to register for the study.

After vaccination, parents are given a flyer with information about the study, and how to sign-up for the study (web address and study specific access code).

The following data are requested.

- general data

1. are MenC and MMR vaccines administered both? If only one, or more than 2, vaccines were given, the child cannot further participate.
2. reporting code
3. date of vaccination
4. batch numbers of administered vaccines (to be recorded at baby clinic)
5. injection sites of administered vaccines (arm/leg/left/right) (to be recorded at baby clinic)
6. registration of email address. Per email address, only one child can participate. For more children in a household/family (twins, triplets,..) separate email addresses are required.
7. accept Lareb privacy rules yes/no. Only proceed if ticked: yes.

- data of reporting parent and child

1. confirm email address
2. child: date of birth
3. child: sex
4. child: height at time of vaccination
5. child: weight at time of vaccination
6. baby clinic: place and street address (choose from list).

- base line data

1. medical history, did your child have: ... (tick if applicable)
 - infections,
 - coughing/dyspnea,
 - skin rash,
 - hypersensitivity or allergy,
 - vomiting and/or diarrhea,
 - other: please specify ...,
 - none of the above.

- concomitant medication

1. Does your child use any medication: if yes: specify the medicine, dose, start date and stop date if applicable

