4.3 Exclusion criteria

- children receiving either MenC or MMR vaccine and not both at the same time
- children that have received simultaneously any other vaccine than MenC and MMR
- children that are vaccinated at baby clinics that do not participate in the study
- children whose parents/caretakers register for the study later than day 4 after vaccination.
- children with parents that are not able or willing to understand/fill the questionnaires in Dutch.

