5.3 Other parameters

The following base line data will be asked, to demonstrate comparability of both study groups. The influence of these potentially confounding characteristics will be addressed in the analysis:

- gender
- weight
- length
- medical history
- house hold size
- daycare and kindergarten

CHAPTER 6. STUDY PROCEDURES AND ASSESSMENTS

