6.1 Schedule per eligible participant

time	actor	activity
- 4 wks	RIVM/DVP	sending letter to parents in region with predefined baby clinics. The letter is with headings of Lareb, and sent by actor.
-4 wks to-1 day	parents	pre-registration at Lareb LIM site, with contact details and planned date of vaccination
Day 1	baby clinic	
 - give MenC and MMR vaccinations - remind parents to the study described in the letter that parents received earlier. - record vaccinations on the study letter from the parents, and recording as usual for adequate registration by RIVM/DVP.
Day 4	parents	latest possibility to register for study, confirmation of date of vaccination
Day 5	Lareb	send questionnaire 1, reminder at day 7
Day 14	Lareb	send questionnaire 2, reminder at day 16
Day 28	Lareb	send questionnaire 3, reminder at day 32
Day 36	Lareb	closure

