9.6 Statistical methods for data analysis

The primary endpoint of the study, fever cases observed within 4 days after vaccination will be analyzed using logistic regression with vaccination groups ("old" / "new" product) and potential confounders as listed in 5.3 as explanatory factors, applying a log link in order to obtain relative risk estimates at the end. Relative risk and its 95% CI of occurrence of fever cases with the "new" and "old" NeisVac-C® product will be calculated from the regression model assessing a potential increase of fever reactions with the "new" product. If the upper limit of the 95% CI is below 1.5 then the "new" product is considered to be non-inferior to the old one as far as fever reaction is concerned.

The secondary endpoints will be analyzed similarly and descriptive without the non-inferiority considerations.

CHAPTER 10. SAFETY REPORTING

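### The baseline medical history is asked after vaccination, up to Day 4, with no pre-vaccination limit, yet it is a covariate in the primary fever model; this may bias the RR, possibly toward non-inferiority

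*Protocol*

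**What the plan says.** Timing. Under 6.3.1, "parents may pre-register for the study by reporting their email address and scheduled vaccination date"; no health question is put at that stage. The same section continues: "At this date, Lareb will send them an email with a link enabling the parents to register for the study". The first item on the registration form is "are MenC and MMR vaccines administered both", so the form is meant for use after the injections. For Day 4 the schedule in 6.1 gives "latest possibility to register for study, confirmation of date of vaccination", and 4.3 excludes "children whose parents/caretakers register for the study later than day 4 after vaccination". By the day numbering in 3.2, Day 4 is also the last day on which fever counts for the primary endpoint.

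The item. Among the baseline data on that form stands "medical history, did your child have: ... (tick if applicable", with boxes for infections, cough or dyspnoea, rash, allergy, vomiting or diarrhoea, other, and none. No recall period or onset date is given. On the same form, height and weight are tied to the time of vaccination, and medication has start and stop dates.

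Use. Section 5.3 lists medical history among the baseline variables and says "The influence of these potentially confounding characteristics will be addressed in the analysis". Section 9.6 fits the primary fever model with the vaccine group and "potential confounders as listed in 5.3 as explanatory factors", using a log link. Non-inferiority is declared if the upper 95% limit of the RR is below 1.5.

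**The concern.** A covariate in a comparison of two vaccines should be fixed before vaccination. This one is recorded afterwards, during the outcome window, and nothing in the protocol's wording confines it to earlier events. Rash, vomiting and diarrhoea are solicited reactions in 5.2 and in questionnaire 1, and a parent of a feverish child might tick the infections box. A tick can therefore be a consequence of the vaccine that shares its cause with fever. Adjusting for such a variable can take out part of the product effect, and randomising clinics gives no protection against that.

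The harmful case is a new product that is more reactogenic, which is what the study was set up to detect. Because no onset date is collected for the history item, earlier and later events cannot be separated at analysis. The comparability check in 9.5 may be affected in the same way.

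**Working it through.** The protocol gives no figure for symptom rates, registration day or how parents will read the item. The check therefore asks what the primary model would estimate under stated assumptions.

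**Inputs from the protocol (9.2, 9.6):** fever 6% in the old group; margin RR 1.5, that is 9% in the new group; 1215 children per group; one-sided alpha 0.025.

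**Assumptions, not in the protocol:** 20% of children have true earlier history, with a fever RR of 1.3; a share L of parents register after symptoms can appear; of these, a share f of parents of febrile children tick a box because of post-vaccination illness, and shares n(new) and n(old) of parents of non-febrile children do. The history enters as one yes/no variable.

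**One case by hand** (L = 80%, f = 50%, n = 15% new and 10% old), per 1000 children:

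- Fever risk without true history: 6%/(0.8 + 0.2 × 1.3) = 5.66% old; 9%/1.06 = 8.49% new. With history, × 1.3: 7.36% and 11.04%.
- Old: ticked = 200 + 45.28 × 0.8 × 0.5 + 754.72 × 0.8 × 0.10 = 278.5, with 14.72 + 18.11 = 32.83 fever cases (11.79%). Unticked = 721.5, with 27.17 cases (3.77%).
- New: ticked = 200 + 67.92 × 0.8 × 0.5 + 732.08 × 0.8 × 0.15 = 315.0, with 22.08 + 27.17 = 49.25 cases (15.63%). Unticked = 685.0, with 40.75 cases (5.95%).
- Crude RR = 90/60 = 1.50. RR among ticked = 15.63/11.79 = 1.33; among unticked = 5.95/3.77 = 1.58.
- Mantel-Haenszel pooling: (49.25 × 278.5/593.5 + 40.75 × 721.5/1406.5) / (32.83 × 315.0/593.5 + 27.17 × 685.0/1406.5) = 44.01/30.66 = 1.44. The log-link model fitted to the same expected counts gives 1.431.

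**False non-inferiority rate** at a true RR of 1.50:

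- SE of log RR = √(0.91/(1215 × 0.09) + 0.94/(1215 × 0.06)) = √(0.00832 + 0.01289) = 0.1457. This treats children as independent.
- Rate = Φ((ln 1.5 − ln adjusted RR)/0.1457 − 1.96).
- With no mis-ticking: Φ(−1.96) = 2.5%, the plan's own alpha.
- At 1.431: Φ(0.0471/0.1457 − 1.96) = Φ(−1.64) = 5.1%.

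**Range from the same model:**

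| L | f | n new / old | Adjusted RR | False non-inferiority |
|---|---|---|---|---|
| 20% | 30% | 7.5% / 5% | 1.496 | 2.6% |
| 50% | 30% | 7.5% / 5% | 1.486 | 2.9% |
| 50% | 50% | 7.5% / 5% | 1.475 | 3.3% |
| 50% | 70% | 15% / 10% | 1.450 | 4.2% |
| 80% | 50% | 15% / 10% | 1.431 | 5.1% |
| 80% | 70% | 15% / 10% | 1.394 | 7.3% |
| 50% | 50% | 5% / 5% | 1.491 | 2.8% |
| 80% | 70% | 10% / 10% | 1.468 | 3.5% |
| 80% | 70% | 10% / 15% | 1.555 | 1.4% |

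In the two rows with equal ticking among non-febrile children, the remaining shift arises because fever itself prompts ticks and is commoner in the new group. In the last row the new product causes fewer of the listed symptoms, and the bias reverses.

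**A second set of assumptions** models a listed symptom directly: present in 10–20% of the old group, fever 3–6 times likelier with it, true history in 0% or 30%, and at most half of symptomatic parents ticking. If the new product raises the symptom 1.5-fold, a true RR of 1.50 becomes 1.37 to 1.50 (false rate 2.5% to 9%). With equal symptom rates it stays at 1.50. With a symptom ratio of 0.67 it becomes 1.50 to 1.63.

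**The case against.** The headings under which the item stands, baseline data and medical history, point to earlier illness, and many parents will read it that way. Post-vaccination events have their own places: the diary, and questionnaire 1 with an onset time for each reaction. Fever is not among the history boxes. The link goes out on the vaccination date and the flyer is handed over that day, so many families may register before any symptom appears. Parents are not told which product was given. The protocol also only summarises the form, which parents complete in Dutch, and how the boxes are coded for the model is commonly left to the SAP.

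Most of this stands as a limit on the size. It does not remove the point. The protocol gives a time reference for height, weight and medication, but none for history. Not knowing the product prevents differential reporting attitudes, but it does not prevent a real difference in symptoms, which is the mechanism here. An SAP could choose the coding, but without onset dates it could not separate earlier from later events. It could only drop the variable, contrary to 9.6.

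A reader might infer that post-vaccination symptoms are certainly adjusted away and that the RR is necessarily pulled toward non-inferiority. The documents do not support that: nothing in them says such symptoms belong in this item, and the direction depends on which product causes more of them.

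**Conclusion.** The flaw is established from the protocol: a covariate of the primary model is collected after vaccination, up to the last day of the fever window, with no pre-vaccination limit and no onset date. Its effect is conditional. Bias toward non-inferiority needs parents to tick post-vaccination symptoms as history, and it becomes material only if the new product causes more of those symptoms.

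For the assumed rates in the main model, a true RR of 1.50 is estimated at about 1.50 to 1.40, with a false non-inferiority rate between about 2.6% and 7% instead of 2.5%. A doubling to about 5% needs inputs near the high end. The second set of assumptions gives similar figures, reaching 1.37 and 9% at its worst when at most half of symptomatic parents tick. Much larger shifts (an RR of 1.20) arise only if every such parent ticks and no child has true earlier history; the documents give no ground for that. The change is worth making because it costs almost nothing and protects the decision in the case that matters most.

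**What to change.** Reword the history item in 6.3.1 so that it covers a stated period before the day of vaccination and excludes anything that began after the injections. Add to 9.6 that only history with onset before vaccination enters the primary model; where that cannot be established, leave medical history out of the adjustment set.

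The cost is one line in the web form and one sentence in the protocol, with no extra participants or contacts. The small downside is that some parents will recall onset imprecisely.

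Moving the block to pre-registration is not advised. Pre-registration opens four weeks before vaccination (6.1), so early registrants could not yet answer for the weeks that follow. The medication item needs no change on this account: it already records start and stop dates, and medication is not in the 5.3 list.

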6.3.2 Questionnaire 1 (4 days after vaccination)

Start question: did your child experience an adverse reaction/event: Y/N.

If N: have other medicines been used: click to add

If Y: which adverse events have occurred

- injection site reaction, if yes
 - o where did the reaction occur: one or both sites: specify arm/leg/left/right
 - o further questions per injection site
 - tick symptoms: red, warm, pain, swelling, indurated patch, blue, itch, other: please specify
 - size: largest possible diameter in centimeters (rounded upwards)
 - onset time after injection
 - treated, if yes specify
 - recovery status, if recovered: when
 - size will be categorised by diameter <2 cm: mild, 2-5 cm: moderate, >5 cm: severe
- fever, if yes
 - what was temperature (max value, rectally measured): __, __°C
 - onset time after injection
 - treated, if yes specify
 - recovery status, if recovered: when
 - impact as experienced by parents, graded as: not-mildly-moderately-very
- skin rash
 - please describe ...,
 - onset time after injection
 - treated, if yes specify
 - recovery status, if recovered: when
 - impact as experienced by parents, graded as: not-mildly-moderately-very
- less appetite
 - onset time after injection
 - treated, if yes specify
 - recovery status, if recovered: when
 - impact as experienced by parents, graded as: not-mildly-moderately-very
- sleeping less
 - please describe ...,
 - onset time after injection
 - treated, if yes specify
 - recovery status, if recovered: when
 - impact as experienced by parents, graded as: not-mildly-moderately-very
- sleeping more/somnolence
 - onset time after injection
 - treated, if yes specify
 - recovery status, if recovered: when
 - impact as experienced by parents, graded as: not-mildly-moderately-very
- listlessness
 - onset time after injection
 - treated, if yes specify
 - recovery status, if recovered: when
 - impact as experienced by parents, graded as: not-mildly-moderately-very

- vomiting
 - onset time after injection
 - how often
 - treated, if yes specify
 - recovery status, if recovered: when
 - impact as experienced by parents, graded as: not-mildly-moderately-very
- diarrhea
 - onset time after injection
 - how often
 - treated, if yes specify
 - recovery status, if recovered: when
 - impact as experienced by parents, graded as: not-mildly-moderately-very
- (febrile) seizures
 - please describe:
 - what was temperature at the time of the seizure:
 - onset time after injection
 - treated, if yes specify
 - recovery status, if recovered: when
 - impact as experienced by parents, graded as: not-mildly-moderately-very
- other reactions (more than 1 additional unsolicited reaction can be added).
 - please describe:
 - onset time after injection
 - treated, if yes specify
 - recovery status, if recovered: when
 - impact as experienced by parents, graded as: not-mildly-moderately-very

For all events together it will be asked :

- was the child seen by a doctor for this complaint.
- did any of the reported events lead to one of the following:
 - o No, if Yes, tick if applicable:
 - hospitalisation
 - immediately life threatening
 - death

Any other data to label the reported AE as serious according to CIOMS criteria will be obtained from free text entries. They will be individually assessed by the Lareb investigator, and further regarded as SAE if applicable.

Co-medication:

- did your child have changes in medication.
Medication listed at Start are shown again and open for editing (start date, stop date, dose, add new)

Characteristics of the household

- how many children are living in your household (including the vaccinee):
choose from list: 1, 2, 3, 4, 5, 6 or more.
- does your child go to guest parents, daycare centre, kindergarten

Any reported complaints that are not resolved will be open to edit in next questionnaires.

In addition, parents are asked to report new events if applicable. All new events are to be entered in a free text field, and will be manually coded.

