5.2 Secondary study parameter(s)

Proportions of children with solicited other systemic and local reactions within 4 days after vaccination with NeisVac-C® and MMR.

The occurrence of the following reactions will be asked actively:

Local (injection site) reactions at the NeisVac-C® and/or MMR injection site

- redness, warmth, pain, swelling, induration, blue, itch

General (systemic) reactions

- rash
- decreased appetite
- less sleeping
- listlessness
- sleepiness/somnolence
- vomiting
- diarrhea
- (febrile) seizures

In addition a free text field is available so that symptoms not listed above can be reported.

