6.5 Measurements

If parents suspect their child to have fever, they are asked to measure body temperature rectally with their own thermometer. It is therefore assumed that all reported temperature values are from rectal measurements. In the current setup of the study there is no possibility to verify if this is actually done. However, we assume that temperature values obtained otherwise, will be similarly distributed over both groups of 'old' and 'new' vaccine recipients.

CHAPTER 7. STUDY PRODUCTS

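### Questionnaire 1 asks about fever only after a general Yes, does not record how temperature was taken, and rounds reaction sizes up before grading them

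*Protocol*

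**What the plan says.** **Entry question.** Protocol 6.3.2 starts Questionnaire 1 with "Start question: did your child experience an adverse reaction/event: Y/N". The No branch reads "If N: have other medicines been used: click to add" and lists nothing else on symptoms. The Yes branch, "If Y: which adverse events have occurred", opens the list of injection-site reactions, fever, rash, appetite, sleep, vomiting, diarrhoea, seizures and other events.

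**Stated intent.** Protocol 5.2 says of the solicited secondary reactions: "The occurrence of the following reactions will be asked actively". It calls them the other reactions, which implies that fever is solicited too, but fever is not on that list.

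**Temperature.** The primary parameter (5.1) is a rectal temperature of 38.0 °C or more within 4 days. The form's only temperature item for fever is "what was temperature (max value, rectally measured"; there is no item on route. Protocol 6.5 asks parents who suspect fever to measure rectally, then concedes: "In the current setup of the study there is no possibility to verify if this is actually done". It goes on: "However, we assume that temperature values obtained otherwise, will be similarly distributed over both groups".

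**Size.** Local reactions are recorded as "size: largest possible diameter in centimeters (rounded upwards" and then graded below 2 cm mild, 2 to 5 cm moderate, above 5 cm severe (6.3.2).

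**The concern.** A parent who answers No to the opening question is never asked whether the child had a fever or any listed reaction. The question does say event as well as reaction, but 3.2 and 6.2 describe the form as asking about adverse drug reactions, so a parent who blames a fever on a cold may well answer No. Later forms do not clearly recover the loss: Questionnaire 2 (6.3.3) asks about events still open and events that began after Questionnaire 1 was completed. What is at stake is primary events, hence power, and the completeness of the solicited secondary data.

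The route problem is different in kind. A parent with an ear or armpit reading can only enter it in a field labelled rectal or leave it out. Equal error in both groups is reassuring in a superiority trial, because it makes a false claim of difference less likely. In a non-inferiority trial, equal false positives push a truly raised risk ratio towards 1, which favours the claim.

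The size rule conflicts with itself: rounding up comes first, and the grade boundary is then applied to the rounded number.

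**Working it through.** **Inputs.** Reference fever risk 6%, margin risk ratio 1.5 (9% in the new-product group) and one-sided alpha 0.025 from 9.2; decision rule, upper 95% limit of the risk ratio below 1.5, from 9.6; 1215 per group from 9.2. The plan's 6% × 1.5 = 9% is consistent. The figure 1215 is taken as given here: a non-inferiority formula of the type named in 9.2, with a 3-point margin, gives 7.849 × 2 × 0.06 × 0.94 / 0.03² = 984, so 1215 is not reproduced, but that is a separate matter.

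**Model.** Observed risk p′ = Se × p + (1 − Sp) × (1 − p), where Se is the share of true fevers recorded and 1 − Sp is the share of non-febrile children wrongly counted. The standard error of the log risk ratio is √[(1 − pA′)/(1215 pA′) + (1 − pB′)/(1215 pB′)]. The probability of declaring non-inferiority is Φ[(ln 1.5 − ln(pA′/pB′))/SE − 1.96]. Children are treated as independent and no covariates are used. Se and Sp are not in the documents; the values below are assumptions.

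**Step 1: the entry question (Sp = 1, same Se in both groups).** The factor Se cancels: (Se × 0.09)/(Se × 0.06) = 1.50 for any Se. The error at a true ratio of 1.5 stays at 2.5%. Power at a true ratio of 1 changes as follows:

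| Fevers missed | Observed risk | SE | Power |
|---|---|---|---|
| 0% | 6.0% | 0.161 | 71% |
| 5% | 5.7% | 0.165 | 69% |
| 10% | 5.4% | 0.170 | 67% |
| 20% | 4.8% | 0.181 | 61% |

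For the first row: ln 1.5 = 0.405; 0.405/0.1606 − 1.96 = 0.565; Φ(0.565) = 0.714.

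Bias would need a different Se by group. At a true ratio of 1.5, Se of 0.8 (new) against 0.9 (old) gives 1.5 × 0.8/0.9 = 1.33; the reverse gives 1.5 × 0.9/0.8 = 1.69.

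**Step 2: false-positive fevers (Se = 1, same Sp in both groups, true ratio 1.5).**

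| Falsely counted | New | Old | Observed ratio | One-sided error |
|---|---|---|---|---|
| 0% | 9.00% | 6.00% | 1.50 | 2.5% |
| 0.5% | 9.46% | 6.47% | 1.46 | 3.8% |
| 1% | 9.91% | 6.94% | 1.43 | 5.5% |
| 2% | 10.82% | 7.88% | 1.37 | 10.2% |

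For the 1% row: 0.09 + 0.01 × 0.91 = 0.0991; 0.06 + 0.01 × 0.94 = 0.0694; ratio 1.428.

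**Step 3: rounding, read as to whole centimetres.**

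| True size | Grade on true size | Recorded | Grade on recorded size |
|---|---|---|---|
| 1.0 cm | mild | 1 | mild |
| 1.1 to 1.9 cm | mild | 2 | moderate |
| 4.1 to 5.0 cm | moderate | 5 | moderate |
| 5.1 to 6.0 cm | severe | 6 | severe |

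Only sizes above 1 and below 2 cm change grade.

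**The case against.** - **The opening question covers events, not just reactions.** No causal judgement is required, 10.1 treats every symptom reported by parents as an adverse event, and 6.2 gives parents a diary for any health event. This stands as a reason to think the loss may be small. It does not remove the routing: a parent who answers No still sees no fever item.
- **The promise of active asking in 5.2 covers the secondary reactions only.** Correct. The contradiction in the text is with those items. For fever the point is lost events, not a broken statement in 5.2. Since 6.5 has temperature taken only when parents suspect fever, removing the entry question can recover only fevers they had noticed.
- **The entry question does not bias the result.** Correct. A reader might infer that it dilutes the risk ratio; step 1 shows that equal under-reporting leaves it unchanged. Parents are not told which product was given (8.1), which makes unequal reporting less likely.
- **The route limitation is disclosed, and its error can run both ways.** Both stand. Non-rectal readings may also miss fevers, which costs power only. The illustrative rates are also not small: 1-2% of non-febrile children would mean that 0.0094/0.0694 = 14% to 0.0188/0.0788 = 24% of reported fevers in the old-product group are false. A reader might infer that the trial's error rate is inflated to 10%; the documents give no rate or direction to support that. What remains is that equal distribution is not by itself a defence in a non-inferiority comparison.
- **The size rule is minor.** Correct. It applies alike to both groups, the stated endpoints are proportions with reactions, and the secondary endpoints carry no non-inferiority claim (9.4, 9.6). It would be wrong to infer that local reactions in general, or severe ones, are over-graded.

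**Conclusion.** The point holds as three separate defects of the form, of unequal weight.

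1. The entry question withholds every solicited item from parents who answer No, contrary to 5.2, and puts primary events at risk. The cost is power: about 71% to 69-61% if 5-20% of fevers are missed. The 71% starting value is a consequence of the sample size under the risk-ratio rule, not of the questionnaire.
2. Route is not recorded, and the reason given in 6.5 for accepting this does not hold for non-inferiority. If equal false positives of 0.5-2% occurred, the one-sided error would be about 4-10% instead of 2.5%. This is an illustration of direction and scale, not an estimate.
3. The rounding rule moves reactions above 1 and below 2 cm from mild to moderate. The 5 cm boundary is unaffected and the outcome is descriptive.

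All miss and false-positive rates are assumptions. The changes are worth making because data that the form does not collect cannot be restored at analysis.

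**What to change.** In Protocol 6.3.2:

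- Remove the opening Yes/No question as a filter. Ask every parent about fever (yes/no, highest temperature) and then each solicited item yes/no.
- Add one tick box for how the temperature was taken (rectal, ear, armpit, forehead, not measured). In 9.6, add a sensitivity analysis that counts only values of 38.0 °C or more reported as rectal. In 6.5, drop equal distribution as the justification. The route remains unverified parental report, so this supports a sensitivity analysis but does not remove the limitation.
- Record diameter in millimetres or 0.5 cm steps and grade on the unrounded value, or reconcile the grade boundaries with rounded-up values.

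The cost is a set of web-form edits, a slightly longer form and one extra analysis. Asking every item directly will also bring in somewhat more minor events.
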